The secondary research objective of this study is to:

1. Evaluate the feasibility of completing the clinical case report form (CRF).

6. Study Outcomes

Primary objectives:

1. Implementation of Extubation Advisor will be considered feasible if:
 - a. >50% of identified eligible patients are enrolled and consented,
 - b. >75% of the time, wave form data is captured,
 - c. >90% of the time, participant clinical data is fully entered into the EA tool,
 - d. >80% of the time, an extubation report is successfully generated and delivered to the attending physician.
2. Usability, perceived value, identified behaviours, perceived barriers and drivers, and perceived impact will be assessed through interviews with RTs and MDs.

Secondary objectives:

1. Completion of the clinical CRFs will be considered feasible if >90% of clinical CRFs are complete.

7. Design

This is an open-label, multi-center interventional Phase 1 study to implement and evaluate perceptions of Extubation Advisor in consenting patients in the intensive care unit.

8. Centers

This study will be conducted at two Ontario academic hospitals: The Ottawa Hospital and Unity Health Toronto.

9. Sample Size and Timeline

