11.1. Study procedure for clinical implementation of Extubation Advisor (EA)

Eligible patients will be identified by RTs or Research Coordinators (RCs) in the ICU for SBT and assessment of extubation. A surrogate will be identified and contacted to provide informed consent on behalf of the eligible patient, after which the eligible patient will be enrolled. No formal screening log will be completed, and RTs/RCs will attempt to identify as many eligible patients as is feasible.

When an eligible patient is identified and enrolled, they will be connected to a bedside or portable monitor displaying ECG and capnography (and other waveforms). Capnography requires a CO₂ module in the monitor, connected to the endotracheal tube by capnography sampling tubing. The RC will first confirm that the patient monitor to be used is compatible with the EA software. An EA laptop will be connected to the monitor through a serial cable. The waveform and vital sign data will undergo processing directly on the laptop using the EA software.

An RT will prepare the patient for an SBT, making sure that the Capnograph (CO₂) module is installed on the monitor, that the CO₂ sensor is on the tubing prior to starting the SBT, and that a CO₂ signal is seen at the monitor. The RT will log on to the EA application and input the patient's demographic and admission information (one-time data entry performed in less than 2 min). The RT will then get feedback from the EA application that it is receiving the vital signs waveform data and that it includes a capnograph (CO₂) waveform (i.e. two separate but related requirements) and displays that the system is ready to go.

With the system indicating it is ready to go, the RT will press the “Start” recording button, initiating the waveform recording. They can then enter the starting (i.e. pre-SBT) ventilator (i.e. PS/PEEP values) and sedation score (i.e. RASS score) into the EA system (~20 sec). The RT will start the SBT by lowering PS/PEEP settings on the ventilator to whatever is ordered by the clinician and clicking the “Start SBT” button in EA to initiate the recording. While the waveforms are being recorded, the RT will complete the rest of the admission information, comorbidities, and extubation readiness checklist (<5 min). At the end of the SBT, the RT will stop the recording (or cancel the SBT if <15 minutes).

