The EA system will process the portions of CO₂ waveforms and vital signs data corresponding to the SBT and proceed to clean and assess the quality of the data, compute variability metrics, and generate a score summarizing the risk of extubation failure.

The RT will then put the PS/PEEP back to normal on the ventilator and complete the SBT Outcome Information and their own impression of the risk of extubation failure (<2 min). The RT will click on the “Generate Report” button, which displays a PDF report on screen. The RT will then review the report with the attending physician and determine whether to proceed with the extubation or not. If desired, the EA report may be emailed to a secure hospital email with the actual report attached for printing, so that

the RT may physically give the report to the attending MD, or place it at the bedside. This process may be repeated every time an SBT is repeated for assessment of a patient’s readiness for extubation, until the patient undergoes planned extubation, or reaches an alternate outcome (self-extubation, direct to tracheostomy, death, transfer to another institution). RTs who complete EA data entry during the SBT will receive a \$10 coffee gift card, limited to a maximum of 3 gift cards per patient for repeated SBTs, as a token of appreciation for their time and expertise.

After a minimum of 72 hours after extubation, the site Research Coordinator will complete a short **Clinical Outcome CRF**, which will include the time of extubation, the outcome of extubation, the need and timing of re-intubation (if present), the need for non-invasive ventilation or high flow heated humidity, all within the 72 hours post-extubation. Last, the Clinical Outcome CRF will include the date of ICU discharge and the status of the patient at that time. Patients who remain hospitalized at 72 hours will be followed via their electronic medical record until hospital discharge.

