12.1. Feasibility evaluation of Extubation Advisor

To evaluate the feasibility of Extubation Advisor implementation we will quantify:

1. The number of identified eligible patients enrolled and consented to capture the proportion of both (a) patients enrolled and (b) patients not enrolled due to patient/caregiver refusal.
2. The proportion of useable recordings and data fully entered, and report on the reasons for failure.
3. The number of reports successfully generated and transmitted to physicians, and report on the reasons for failure.

To evaluate the feasibility of completing clinical CRFs we will quantify the number of clinical CRFs that have been deemed complete.

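### Criteria 1b to 1d have no stated unit or denominator, and the data described would support a rate only among SBTs where Extubation Advisor was started, which can err only towards feasible

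*Combined protocol and SAP*

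**What the plan says.** **Criteria.** Section 6 (Study Outcomes) calls implementation feasible if, among other things:
- 1b: ">75% of the time, wave form data is captured"
- 1c: ">90% of the time, participant clinical data is fully entered into the EA tool"
- 1d: ">80% of the time, an extubation report is successfully generated and delivered to the attending physician"

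**Evaluation.** Section 12.1 covers 1b and 1c with "The proportion of useable recordings and data fully entered, and report on the reasons for failure". For 1d it gives a count: "The number of reports successfully generated and transmitted to physicians, and report on the reasons for failure". Neither section names a denominator.

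**Procedure (section 11.1).** The coordinator confirms that the monitor is compatible. The RT logs on and enters demographic and admission data, and EA then confirms that it is receiving waveforms that include CO2. Recording follows: "With the system indicating it is ready to go, the RT will press the" start button. Afterwards, "At the end of the SBT, the RT will stop the recording (or cancel the SBT if <15 minutes" have elapsed). For later SBTs, "This process may be repeated every time an SBT is repeated for assessment".

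**Data sources.** Under section 14 the study database combines EA report data, waveforms captured during the SBT and the case report form. The outcome CRF in section 11.1 covers extubation, re-intubation, respiratory support, ICU discharge and status. It has no list of SBTs. Section 11.1 also says that no formal screening log is kept.

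**The concern.** The research question is whether EA can be implemented in the ICU. An SBT in an enrolled patient where EA was not tried, where the set-up never reached the ready state, or where the run was abandoned for a technical reason is an implementation miss. If such SBTs leave no record, they cannot enter a denominator, and the rate becomes success given that EA was already running.

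The three criteria are not affected alike. The CO2 check bears mainly on 1b and 1d, because some of the data behind 1c are entered before it. Skipped repeat SBTs bear on all three.

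Three of the four primary feasibility criteria are involved. Section 2.1 says that the study is meant to inform a future randomized trial and each centre's decision on adopting EA. The direction of error is known: removing misses from the base can only raise the rate.

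**Working it through.** **The plan's own figure.** Section 9.1: 24 patients per month × 3 months = 72, and 72 × (1 − 0.20) = 57.6, which rounds to the stated 58. It reproduces, but it counts patients with complete CRFs and gives no base for 1b to 1d.

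**Inputs.**
- Thresholds from section 6: 75% (1b), 90% (1c), 80% (1d).
- Assumption: the SBT rate of the 2019 study in section 2.1 applies, 151/117 = 1.29 per patient.
- Assumption: that study's 92% report generation is the success rate among EA-started SBTs.
- Unknown: coverage, meaning the share of SBTs in enrolled patients on which EA was started.

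**Formulas.** All-SBT rate = coverage × success among started SBTs. Break-even coverage = threshold ÷ success among started SBTs.

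**Break-even coverage at 92% success.**
- 1d: 0.80/0.92 = 0.870, so it fails at about 87% coverage or lower.
- 1b: 0.75/0.92 = 0.815, so it fails at about 81.5% or lower, if capture equals report generation. A report needs captured waveforms, so capture can only be equal or higher, and the true break-even for 1b can only be equal or lower.
- 1c: no success rate is given. Even with perfect entry at every started SBT, 0.90/1.00 = 90% coverage or lower fails.

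**Range for 1d.**

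| Success among started SBTs | Break-even coverage |
|---|---|
| 85% | 94% |
| 92% | 87% |
| 95% | 84% |
| 100% | 80% |

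**All-SBT report rate at 92% success.**

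| Coverage | All-SBT rate | Against >80% |
|---|---|---|
| 90% | 83% | passes |
| 80% | 74% | fails |
| 77% | 71% | fails |
| 60% | 55% | fails |

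The 77% row is EA at each patient's first SBT only: 72 × 1.29 = 92.9, about 93 SBTs, and 72/93 = 77%. The EA-started rate is 92% in every row.

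**In counts.** Suppose instead that the 93 are EA-started SBTs, with 0.92 × 93 = 85.6, about 86 reports.
- With 14 further SBTs unrecorded, 86/107 = 80.4%. With 15, 86/108 = 79.6%, and 1d fails.
- With 21 unrecorded, 86/114 = 75.4%. With 22, 86/115 = 74.8%, and 1b fails on the same equality assumption.

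The 15 and 22 are the counts at which the conclusion changes. They are not estimates of what will happen.

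**The case against.** A reader might infer that the plan scores 1b to 1d only on EA-started SBTs. No passage says so. The denominator is undefined, and section 12.1's commitment to give reasons for failure is compatible with counting no-signal and cancelled attempts as failures. What stands is that no record of those attempts is clearly described, and that reasons for failure cannot cover SBTs where EA was never tried.

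A reader might also infer that EA is optional throughout. The permissive wording governs repeat SBTs only; the initial procedure is directive. Repeat capture is also encouraged, by gift cards for up to three SBTs per patient (section 11.1) and extra site funding for multiple SBTs (section 11.2). This makes poor coverage less likely, but it does not make coverage measurable.

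Nor is a missed SBT always invisible. Section 11.2 requires that the last SBT before extubation gave a report shown to the physician, or the patient is not complete, and completeness feeds the secondary >90% criterion. That is a partial safeguard. It looks at one SBT per patient and does not feed 1b to 1d.

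Finally, it would go too far to say that EA will miss many SBTs. The documents give no rate of skipped, failed or cancelled runs, and the 2019 figures may themselves count captured SBTs only. The CRF forms and the monitoring plan are not reproduced, so the missing log is a statement about the text supplied.

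**Conclusion.** The point holds as a gap in definition and data capture. The unit and denominator of 1b to 1d are not stated, and the sources described would in practice support only a rate among EA-started SBTs. Such a rate is never lower than the all-SBT rate, so any error favours feasibility.

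The size is illustrative. At 92% success among started SBTs, 1d changes from pass to fail once coverage is about 87% or lower (80% to 94% as success runs from 100% to 85%). Criterion 1b changes at about 81.5% or lower if capture equals report generation. Both rest on carrying the 2019 success rate over as an EA-started rate, and actual coverage is unknown. The documents do not show that the criteria would fail, only that the planned data could not tell. It should be settled before enrolment, because set-up failures and cancellations may be hard to reconstruct afterwards.

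**What to change.** 1. In sections 6 and 12.1, define the denominator of 1b, 1c and 1d as all SBTs done for extubation assessment in enrolled patients, from consent until planned extubation or one of the other outcomes listed in section 11.1. State 1d in section 12.1 as a proportion.
2. Have the research coordinator log one line per SBT from the chart: EA attempted, ready state reached, cancelled and why, report produced and delivered.
3. Count unattempted SBTs, failed set-ups and technical cancellations as failures. Show separately the SBTs stopped before 15 minutes because the patient did not tolerate them.
4. Report the rate among EA-started SBTs as a secondary figure.

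EA need not be made mandatory at every repeat SBT; it is enough that SBTs without it are counted. The cost is about 90 to 120 log lines over the study (93 to 115 in the scenarios above), a wording change in two sections, and possibly lower headline rates.

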11.2. Definition of complete CRF

A patient and their data collection will be deemed “complete” if **(1)** the patient’s last SBT prior to extubation resulted in the generation of an EA report that was shown to the physician, and **(2)** the clinical outcome CRF is complete. In cases where the completion of the “Clinical Outcome Information” CRF is not possible (e.g. when extubation did not follow the generation of an EA report, if a tracheostomy was performed, etc.) the patient will remain enrolled, but results will not be included in final analyses, and those patients will be deemed incomplete. Funding will thus prioritize complete patient data collection. Additional funding will be provided if multiple SBTs are captured in the same patient.

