9.1. Sample size for clinical implementation of Extubation Advisor

We will enroll a total of 72 patients, including patients both with and without COVID-19, able to provide informed consent, through a surrogate. We anticipate that 1 patient will be enrolled per week at each ICU (average of 24 patients per month), with enrolment occurring over a period of 3 months, and that there will be a 20% loss due to protocol deviation, loss of data, inability to provide a complete extubation CRF, etc. This will leave 58 patients with complete CRFs, which we anticipate 9-10 will experience extubation failure.

This will allow a robust evaluation of feasibility outcomes, including consent rates, waveform and clinical data collection, and report generation – see section 5 above). Over several months, individual clinicians will likely be in the ICU 3-5 weeks, and be exposed to 5-10 patients with EA, which we feel is adequate to provide their initial perceptions of usability.

9.2. Sample size for mixed-methods analysis.

We will interview up to 10-15 physicians and 10-15 respiratory therapists, distributed equally among participating sites, up to a maximum of 2 times. Repeated interviews will be conducted only when the study team deems the tool to have changed enough to warrant being seen again by the same people. Enrolment of 10-15 physicians and 10-15 respiratory therapists will be sufficient for thematic data saturation based on previous evidence supporting sizes of 10 to 13 participants in both theory-based and non-theory-based qualitative interviews^{34,35}.

10. Eligibility

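### Section 11.2 drops patients with no possible outcome CRF from unspecified final analyses without exempting the Section 6 feasibility criteria, and the base for the >90% CRF criterion is not fixed

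*Combined protocol and SAP*

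**What the plan says.** Section 11.2 of the combined protocol and SAP calls a patient complete when two things hold: the last SBT before extubation produced a report that the physician saw, and the outcome CRF is complete. Where that CRF is not possible, "the patient will remain enrolled, but results will not be included in final analyses, and those patients will be deemed incomplete". The examples given are no extubation after a report, and tracheostomy.

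Section 11.1 treats such endings as ordinary. The EA process may be repeated until planned extubation or until the patient "reaches an alternate outcome (self-extubation, direct to tracheostomy, death, transfer to another institution". It ties the outcome form to extubation: "After a minimum of 72 hours after extubation, the site Research Coordinator will complete a short" outcome CRF.

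Section 6 sets the secondary criterion: "Completion of the clinical CRFs will be considered feasible if >90% of clinical CRFs are complete". Section 12.1 says only that "we will quantify the number of clinical CRFs that have been deemed complete", which is a count without a denominator. For primary criterion 1d (report generated and delivered more than 80% of the time), Section 12.1 promises "The number of reports successfully generated and transmitted to physicians, and report on the reasons for failure". Neither section states whether the unit is the patient or the SBT.

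Section 9.1 plans 72 patients and expects that "there will be a 20% loss due to protocol deviation, loss of data, inability to provide a complete extubation CRF, etc". It continues: "This will leave 58 patients with complete CRFs".

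**The concern.** The exclusion in Section 11.2 has no stated limit, and no section says that the feasibility criteria stand outside it. Applied as written, it removes patients from feasibility rates because of what happened after the report, including the clinical decision that the report is meant to inform. A patient whose report was produced, delivered and read, and who was then not extubated, is a success for report delivery. Yet this is the first example of a patient to be dropped.

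The CRF criterion has a second gap. Its base could be all enrolled patients or only those for whom a CRF fell due after extubation. Section 12.1 counts forms deemed complete, a status that Section 11.2 defines for the patient and all their data rather than for the form alone.

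A pass/fail threshold is informative only if the rate compared with it is fixed beforehand. The results are meant to inform the design of a later randomized trial. All-enrolled rates can still be recovered, since the patients stay enrolled and Section 17(b) asks for a report covering all subjects. What is not fixed is which rate is held against the threshold.

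**Working it through.** **Inputs.** Enrolled: 72 (Section 9.1). Planned loss: 20%, several causes pooled (9.1). Patients with complete CRFs: 58 (9.1). CRF threshold: >90% (Section 6). Report threshold, criterion 1d: >80% (Section 6). Phase I report generation: 92%, single centre (Section 2.1).

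**Step 1: reproduce the plan's figure.** 72 × (1 − 0.20) = 57.6, which rounds to the stated 58. Planned losses: 72 − 58 = 14.

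**Step 2: CRF criterion, all enrolled as base.** 58/72 = 80.6%. The threshold is 0.90 × 72 = 64.8, so at least 65 complete patients are needed (65/72 = 90.3%). The plan's own expectation is 7 short.

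**Step 3: CRF criterion, CRFs due after extubation as base.** Let k be the number of the 14 losses who were never extubated, so that no CRF fell due. The rate is 58/(72 − k). It exceeds 0.90 when 72 − k < 58/0.90 = 64.4, that is, when k is at least 8.

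| k | Rate | >90%? |
|---|---|---|
| 0 | 58/72 = 80.6% | no |
| 7 | 58/65 = 89.2% | no |
| 8 | 58/64 = 90.6% | yes |
| 14 | 58/58 = 100% | yes |

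Section 9.1 does not divide the 14 losses by cause, so k is unknown and the whole range is shown.

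**Step 4: criterion 1d.** The smallest passing counts are 58/72 (80.6%) and 47/58 (81.0%). Assume one report per patient, independent patients, a true rate of 92%, all 14 losses excluded, and exclusion unrelated to delivery. The binomial chance of passing is then 0.9995 on 72 and 0.998 on 58, and the two bases give different verdicts in about 0.2% of studies. The 92% covers generation only, whereas 1d also requires delivery. If exclusion is related to delivery, the direction of the effect is not determined, because some excluded patients will have had a delivered report.

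**Step 5: criterion 1a.** Enrolment and consent are unaffected, because the excluded patients remain enrolled.

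**The case against.** The best counter-argument is that context narrows the exclusion. The sentence sits in a procedures section, next to remarks on site funding, and Section 9.1 links complete CRFs to the expected number of extubation failures. The results to be left out could therefore be extubation-outcome results only. Section 12.1 deals with feasibility separately and asks for the reasons behind failed recordings, data entry and reports, which cannot be given if failures are discarded. Calling patients incomplete also suggests that they stay in the base as failures. This is a fair reading and may be the intended one. But it is only implied, and the sentence that calls these patients incomplete also removes their results from the final analyses.

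It can also be said that the 20% is a planning allowance that pools protocol deviation, data loss and CRF problems, whereas the exclusion applies only where the CRF is not possible. That stands. The 80.6% is the planned share of complete patients, not a pure rate of CRF completion, and the due-base verdict depends on a split that the plan does not give.

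A reader might infer that the criterion would be reported as 100%, from 58/58. That base counts only patients already classed as complete, so every result would pass and the threshold would mean nothing. The documents do not support it as a realistic choice. Nor do they show that the sponsor intends to use a favourable base.

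**Conclusion.** The point holds as a matter of definition and should be fixed before analysis. An unqualified exclusion, triggered after the report, is not separated from the feasibility criteria, and the base of the >90% CRF criterion is not stated. With all enrolled patients as base, Section 9.1's own expectation (80.6%) falls short of Section 6's threshold. With CRFs due after extubation as base, the verdict changes between 7 and 8 of the 14 losses leaving the denominator. Both statements take the planning figures as if observed, and the second also rests on an unknown split.

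A reader might infer that primary criterion 1d would change verdict too. The documents do not support that: it is exposed to the same rule, but at the only rate they supply it passes comfortably on either base. A change would need delivery close to 80%, a rate that they do not predict. The demonstrated effect on a verdict is therefore confined to one secondary, descriptive criterion, and it is conditional there.

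**What to change.** - **Section 11.2:** limit the exclusion to summaries that need an extubation outcome, and state that it does not apply to the Section 6 criteria.
- **Sections 6 and 12.1, criteria 1b to 1d:** state that the base is every SBT attempted with EA in all enrolled patients. Count as failures the SBTs where recording never started, or where capture, data entry, generation or delivery failed. Show SBTs cancelled before 15 minutes separately.
- **Sections 6 and 12.1, CRF criterion:** name one primary base, all enrolled patients, keeping Section 11.2's definition of complete. Show the rate among extubated patients alongside it.
- **Sections 6 and 9.1:** reconcile the >90% criterion with the planned 20% loss, which on the all-enrolled base implies a miss.

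The cost is wording in four sections and no extra patients. Sites must note SBT attempts where recording never started, which the promise to report reasons for failure largely implies already. The downside is that the reported CRF rate may be less favourable than on a narrower base.
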